8.3 Study Conclusion

The Study Conclusion page of the CRF will be completed for all subjects whether they completed all study procedures or if they were discontinued from the study early. If the subject discontinued early, at any point during the study, the primary reason for withdrawal should be recorded on the Study Conclusion page.

If a subject has any clinically significant, study-related abnormalities or AEs at the end of the study, the GSK CH medical monitor (or designated representative) should be notified and, the subject may be asked to remain at the clinical site or be asked to return for a follow-up visit to ensure any issue is resolved or deemed not clinically significant.

8.4 Follow-up Visit/Phone Call

The study site may contact a subject to follow up an AE post-study completion/withdrawal and, in some circumstances, request they return to the site for additional follow-up visits (final safety assessments). If needed, additional examinations may be carried out at such visits.

9 STUDY ASSESSMENTS

Every effort should be made to ensure that protocol required tests and procedures are completed as described. However, it is anticipated that from time to time there may be circumstances, outside the control of the investigator, that may make it unfeasible to complete an assessment. In these cases, the investigator must take all steps necessary to ensure the safety and wellbeing of the subject. When a protocol required assessment cannot be performed, the investigator (or designee) will document the reason for the missed assessment as a protocol deviation and any corrective and preventative actions that he or she has taken to ensure that required processes are adhered to as soon as possible. The Sponsor must be informed of any missed assessments in a timely manner.

9.1 Screening Assessments

Screening assessments will be performed by appropriately trained staff/clinical examiners at the times, and in the order, defined in the [Study Procedures](#) section of this protocol.

9.1.1 Denture Bearing Tissue Score

The denture bearing tissue score ([Kapur, 1967](#)) will be assessed by the investigator and recorded for the maxillary denture only on the appropriate CRF. A score will be allocated for each of the criteria (ridge shape, tissue resiliency and location of border attachment) according to [Table 9-1](#). There are no eligibility requirements associated with this measure in this bite force trial.

Table 9-1 The denture bearing tissue score ([Kapur, 1967](#))

Score	Ridge Shape	Tissue Resiliency	Location of Border Attachment
1	Flat	Flabby	Low
2	V-shaped	Resilient	Medium
3	Shaped between U and V	Firm	High
4	U shaped	-	-

9.1.2 Kapur-Olshan Index (Well Fitting Assessment)

Only the maxillary denture will be examined for retention and stability during screening using the Olshan modification of the Kapur Index (Olshan et al., 1992, Kapur, 1967) by an examiner with expert knowledge of prosthodontics. This assessment is to be performed with no denture adhesive present.

Retention:

With gloved hands, the examiner will attempt to unseat the maxillary denture by applying an opposing vertical force at the canine/lateral incisor region of the denture. The examiner will score retention as 0 - 5 using the following criteria:

- 5= Excellent- denture offers excellent resistance to vertical pull and lateral force.
- 4= Very Good- denture offers very good resistance to vertical pull and lateral force.
- 3= Good- denture offers moderate resistance to vertical pull and lateral force.
- 2= Fair- denture offers moderate resistance to vertical pull and little or no resistance to lateral force.
- 1= Poor- denture offers slight resistance to vertical pull and little or no resistance to lateral force.
- 0= No retention- when the denture is seated in place, it displaces itself.

Stability:

With gloved hands, the examiner will attempt to rock the seated maxillary denture by placing alternate horizontal force at the cuspid and contralateral molar regions of the upper denture. The examiner will score denture stability as 0 - 4 using the following criteria:

- 4= Excellent- when denture offers excellent stability; demonstrates no rocking on its supporting structures under pressure.
- 3= Good- when denture offers good stability; demonstrates very slight rocking on its supporting structures under pressure.
- 2= Fair- when denture offers sufficient stability; demonstrates slight rocking on its supporting structures under pressure.
- 1= Poor- some stability; when a denture base demonstrates moderate rocking on its supporting structures under pressure.
- 0= No stability- when a denture base demonstrates extreme rocking on its supporting structures under pressure.

9.1.3 Well Made assessment

The maxillary denture, and mandibular denture if present, will be assessed for this study.

Clinical Acceptability

Only dentures having adequate (as judged by an examiner with expert knowledge of prosthodontics) vertical dimension, freeway space, horizontal occlusal relationships and border extension will be considered clinically acceptable. For the maxillary denture, the examiner will indicate acceptable or unacceptable on the CRF.

Denture Finish and Contour

The contour and finish of the denture will be examined. Only dentures with acceptable (as judged by an examiner with expert knowledge of prosthodontics) porosity, tissue surfaces,

polished surfaces, color and thickness will be accepted. For the maxillary denture, the examiner will indicate acceptable or unacceptable on the CRF.

9.1.4 Maxillary Bite Force Assessment (Training and Qualifying Bites)

The mandibular denture, if present, will be stabilized using denture adhesive ([Appendix 15.2](#)). Subjects will then be instructed in the execution of the BF assessment. The subject will be instructed sit and hold their head in a natural position so that the occlusal plane is parallel to the floor. The examiner will stand in front of the subject holding the bite force transducer parallel to the floor at a comfortable level for the subject. In order to facilitate insertion of the BF transducer, the examiner may angle the BF plates as necessary. To prevent cross contamination between subjects, the examiner will place a clean finger cot over the bite force plates in addition to a clean infection control syringe sleeve over the transducer hand piece. The examiner will insert the bite force plates into the subject's mouth and then ensure that the muscles of mastication are relaxed. The examiner will signal the subject to bite until movement on the maxillary denture is observed at which time they will be instructed to release their bite. If, in the opinion of the examiner, the subject will be unable to successfully complete the required BF system training, the subject will be withdrawn from the study.

Should a bite described below be compromised through a methodological or instrumental error, e.g. by misalignment of the transducer in the mouth, the bite can be repeated at the examiner's discretion.

9.1.4.1 Training Bites

During the Screening visit, the examiner will record a triplicate bite force measurement without any denture adhesive. The performance of training bites will be confirmed in the CRF (individual training bite values will not be recorded).

9.1.4.2 Qualifying Bites

Four further BF measurements, known as qualifying bites, will be performed after the training bites. All 4 qualifying bites must be ≤ 9 lbs. In addition, two out of the 4 qualifying bites must be reproducible within ± 2 lb for a subject to be eligible to participate in the study. This will form the subject eligibility/adherence for study continuance (as per Inclusion criterion 6).

9.2 Efficacy Assessments

The following efficacy assessments will be performed by appropriately trained staff/clinical examiners, at the times and in the order defined (as much as possible) in the [Study Procedures](#) section of this protocol.

If in the opinion of the examiner a subject is between defined grades/scores, a conservative approach should be used to provide the final score. The same approach should be applied throughout the study to ensure consistency in the grading of the scores at all timepoints.

9.2.1 Treatment Day (Visits 2-5) Maxillary Bite Force Assessments (Practice, Baseline and Test Bites)

All BF measurements will be conducted by an examiner (preferably by the same examiner throughout the study) that is fully trained in the use of the BF transducer equipment and is experienced in performing BF measurements. Prior to any BF measurements on treatment days (Visit2-5) the mandibular dentures, if present, will be stabilized ([Section 9.1.4](#)).

9.2.1.1 Practice Bites

On each treatment day, the examiner will take 3 BF measurements without denture adhesive, known as practice bites. The purpose of this is to re-familiarize the subject with the BF transducer equipment and how to perform a valid bite.

9.2.1.2 Baseline Bite

Following the practice bites, a 4th bite will be performed, without any denture adhesive, and this will be the baseline pre-treatment BF measurement.

For a subject to be eligible, 1 of the 3 practice bites must be within ± 2 lbs of the baseline pre-treatment bite. In addition, only subjects whose pre-treatment baseline BF is ≤ 9 lbs will be eligible to proceed in the study. If a subject does not meet these criteria at any of the treatment day visits, they will be discontinued from the study.

9.2.1.3 Test Bites

Additional BF measurements will be taken at 0.5, 1, 3, 6, 9 and 12 hours after application of test adhesive (or no adhesive as per randomization schedule). The reading should be taken no earlier than the stated time, and a tolerance of 5 minutes for the 30 min bite and 10 minutes for all other time points is acceptable.

9.3 Safety and Other Assessments

9.3.1 Oral Soft Tissue Examination

Where possible, this procedure should be conducted by a single dental examiner or clinically qualified designee for all subjects for all visits. The OST examination will be accomplished by direct observation and palpation, using retraction aids as appropriate, and will include examination of the oral labial mucosa (including lips), buccal mucosa, and mucogingival folds, edentulous gingival mucosa, including any gingival mucosa surrounding any mandibular dentition as applicable, hard palate, soft palate, tonsillar area, pharyngeal area, tongue, sublingual area, submandibular area and salivary glands. The results of the examination will be recorded in the CRF as either normal or abnormal with details of any abnormalities. Any abnormality or worsening of a pre-existing condition observed by the clinical examiner or reported by the subject from the OST examination carried out at Screening, Visit 1, will be recorded as an AE.

The OST examination will be performed at the start of Screening, Visit 1, before any adhesive application (if required for mandibular stabilization) and/or commencement of screening BF assessments, and again at the end of the day following denture and adhesive removal (if applied for mandibular stabilization).

During the study treatment periods (Visit 2 to 5), an OST examination will be performed prior to adhesive application (or no adhesive as per randomization schedule) and also after the completion of all efficacy assessments at the end of each test day following denture and adhesive removal, and all findings will be recorded in the CRF. The OST examination should be performed by a suitably qualified dental professional with expertise in prosthodontics. The subject may be asked to perform an oral rinse with water to remove debris from the mouth before or during this examination, at the examiner's discretion.

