An oral soft tissue (OST) examination will be conducted at each treatment visit before treatment is applied to ensure the subject's oral health is sufficient to allow the subject to complete the assessments at that visit. A further OST exam will be performed at each treatment visit after the completion of assessments to assess for possible AEs. Similarly an oral hard tissue (OHT) examination will be performed at the start (visit 1) and end (visit 5) of the study to assess for potential AEs.

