5.5.3 Medication and Treatment Restrictions

- The details of current and concomitant medications will be collected, and subjects will be allowed to participate if these medications are judged to be non-interfering by the investigator as per inclusion and exclusion criteria.
- Subjects will not be permitted to have any routine dental/denture work performed during the time that they are in the study, unless it is for emergency treatment that should not be delayed. This is to ensure that the denture fit will not be altered during the study.
- If a subject uses denture adhesive as part of their normal routine, then they can continue using the adhesive between treatment visits, but they should not change the routine of adhesive use during the course of the study.
- Subjects will be instructed to report to the study site on treatment visit days (Visits 2-5) without denture adhesive on their maxillary denture and mandibular denture (if present).

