- Medical or surgical procedure (e.g. endoscopy, appendectomy) is not the AE. The condition that leads to the procedure is an AE (e.g. appendicitis).
- Situations where an untoward medical occurrence did not occur (social and/or convenience admission to a hospital).
- Anticipated day-to-day fluctuations of pre-existing disease(s) or condition(s) present or detected at the start of the study that do not worsen.

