4.4.1 Adverse Events and Serious Adverse Events

Adverse events (AEs) will be categorized as oral or non-oral by the examiner prior to database lock. AEs will be deemed to be treatment emergent if they occur after the first supervised use of the randomized treatment. No specific risks or anticipated adverse device effects are expected to be observed within this study, however all AEs and medical device incidents will be assessed to evaluate the tolerability and safety of the treatments. No formal statistical analyses of AEs will be performed. AEs will be listed in Listing 2. Serious Adverse Events (SAEs) will be listed in Listing 3.

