4.4.3 Oral Soft Tissue Examination

Oral soft tissue exam (OSTE) will be collected in the study database but will not be reported in tables or listings. Any treatment emergent abnormal findings will be included in the AE listing. No formal statistical analyses of OSTE will be performed.

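### The safety plan has no period-level baseline for oral soft tissue findings and no output by treatment, so it cannot show the local tolerability of each experimental adhesive against no adhesive

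*Protocol*

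**What the plan says.** The safety objective (Protocol section 3, SAP 1.2) is the local tolerability of the two experimental adhesives. Protocol 12.3.3 assesses it through oral AEs, which include treatment-emergent OST abnormalities.

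- **Reference exam.** Protocol 9.3.1 covers any abnormality, or worsening of a pre-existing condition, seen by the examiner or "reported by the subject from the OST examination carried out at Screening, Visit 1, will be recorded as an AE". No other reference exam is named.
- **Emergence.** Protocol 12.3.3 and SAP 4.4.1 share one rule: "AEs will be deemed to be treatment emergent if they occur after the first supervised use of the randomized treatment". Neither gives a rule by period.
- **Exams available.** Under Protocol 9.3.1, Visits 2 to 5 each have an OST exam before application and another after the dentures and adhesive are removed, and "all findings will be recorded in the CRF". Protocol 4.2 gives the purpose of the first as confirming that "oral health is sufficient to allow the subject to complete the assessments at that visit". It gives the second the task of looking for possible AEs. The two are not linked.
- **Reporting.** SAP 4.4.3: "Oral soft tissue exam (OSTE) will be collected in the study database but will not be reported in tables or listings". Its next sentence sends treatment-emergent abnormal findings to the AE listing.
- **Basis.** Protocol 12.2 and SAP 4.1.3 base the Safety population on the treatment actually received.

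**The concern.** Each subject receives all four treatments in turn, with gaps of 1 to 28 days. Habitual adhesive users are told that "they can continue using the adhesive between treatment visits". A finding at the end of Visit 4 could reflect that day's product, an earlier period's product, the subject's own adhesive, or a condition already present at Screening. The pair of exams on the test day gives the most direct evidence on that day's product, and the plan does not use the pair for this.

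At stake is whether the study report can say anything about how each experimental adhesive was tolerated relative to no adhesive. Efficacy is handled differently: the primary model carries both a subject-level and a period-level baseline. Safety has no counterpart to the period-level term.

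**Working it through.** The plan states no figure on this point, so there is none to reproduce. The check has three steps.

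**1. Do the two possible references give different answers?** Code each exam as normal (N) or abnormal (A), and judge the end-of-day exam under two rules: new since Visit 1, or new since that visit's pre-application exam. Grades of severity are ignored.

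| Visit 1 | Pre-application | End of day | New since Visit 1 | New since same-day pre |
|---|---|---|---|---|
| N | N | N | no | no |
| N | N | A | yes | yes |
| N | A | N | no | no |
| **N** | **A** | **A** | **yes** | **no** |
| A | N | N | no | no |
| **A** | **N** | **A** | **no** | **yes** |
| A | A | N | no | no |
| A | A | A | no | no |

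The rules disagree in 2 of 8 patterns.

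- *A, N, A.* Exclusion criterion 13 bars a Visit 1 OST finding only if the investigator thinks it could interfere with the study, so such subjects can be enrolled. The finding clears, then returns on a test day, but is no worse than at Visit 1. Protocol 10.1 pulls both ways. Among events that are not AEs it lists "Anticipated day-to-day fluctuations of pre-existing disease(s) or condition(s) present or detected at the start of the study that do not worsen". Among events that are AEs it lists exacerbation of an intermittent condition, including greater frequency. Recording is left to judgement. If no AE is recorded, the finding appears in no output.
- *N, A, A.* After Period 1 this is a treatment-emergent AE, although it was present before that day's product was applied.

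**2. How far is Visit 1 from the exposure of interest?** Screening is 1 to 28 days before first treatment (Protocol 8.1), and the three gaps between treatment visits are 1 to 28 days each (8.2.1). Visit 1 to Visit 5 therefore spans between 4 × 1 = 4 and 4 × 28 = 112 days. The upper value is a scheduling limit, not an expected interval. Test-day exposure is about 12 hours. Visit 1 itself has two OST exams, at the start and end of the day, so even the named reference is not unique. Same-day pairs number 4 × 42 = 168 to 4 × 45 = 180 for 42 to 45 subjects completing all periods. These are pairs of exams, not misclassified findings.

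**3. Can the planned output attach a finding to an adhesive?**

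| Output | What it holds | What it lacks |
|---|---|---|
| OST tables or listings | none planned | everything except findings that become AEs |
| SAP Table 14 | separate rows for oral AE and TEAE, one Total column | columns by treatment; an oral TEAE row |
| SAP Listing 2 | start and stop dates; oral, TEAE and product-related flags | treatment, period, visit |

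No planned table or listing shows oral findings by adhesive, although the population definition calls for analysis by treatment received.

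**The case against.** The strongest case against is that the safety information is captured. Every new abnormality after consent is an AE, with a start date and a mandatory causality assessment that weighs timing and alternative causes (Protocol 10.3 and 10.5.2). Treatment emergence is not attribution. No formal AE analysis is planned, and efficacy is untouched. The 9.3.1 sentence is also loose: it can mean change compared with Visit 1, or findings from Visit 1 onward.

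Much of this stands, and it rules out several stronger readings that a reader might infer.

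- *That the trial will miscount events for the adhesive worn that day.* No count by adhesive is planned, so there is none to be wrong. The gap is the missing count.
- *That a lesion arising between visits becomes a false event.* It is a valid AE. If the pre-application exam shows it, its timing is documented.
- *That Protocol 10.1 excludes a recurrence of a Visit 1 finding.* The wording on greater frequency may capture it, so omission is possible but not certain.
- *That OST findings are not reported at all.* Treatment-emergent ones reach the AE listing.
- *That anything present before application should be set aside as arising between visits.* A delayed reaction to the previous period's product would look the same, and AE collection runs to 5 days after the last administration.

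What the objection does not supply is a same-day baseline under either reading of 9.3.1, or any output by treatment. Dates and causality calls sit in a listing that does not identify the period or the product.

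**Conclusion.** The point holds as a gap in definition and reporting. The data needed are collected, but the plan lacks a rule linking the two exams of a treatment visit and an output arranged by treatment. As written, the tables and listings cannot set the local tolerability of either experimental adhesive beside no adhesive, which is what the safety objective needs. One pattern (present at Visit 1, absent pre-application, present at end of day) may go unrecorded.

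How often that would happen cannot be estimated, because the documents give no OST abnormality rate. The conclusion assumes that the table shells, which the SAP labels as rough drafts, are what will be produced. Even the same-day comparison is not a pure measure of the maxillary product: Super Poligrip Free may be used on a mandibular denture on any test day, including the no-adhesive day. This is another reason to show results by treatment with no adhesive alongside. The change is worth making before database lock. It does not affect the primary analysis.

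**What to change.** Keep the existing AE recording and causality rules. Then:

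1. In SAP 4.4.1 and 4.4.3, define a period-level OST change: absent or milder at that visit's pre-application exam, and present or worse at its end-of-day exam. Summarise it by treatment received, including no adhesive. The CRF records normal or abnormal with details, so the SAP should say how milder and worse are judged from those details.
2. In Table 14, add a row for oral TEAEs and report it by treatment received.
3. In Listing 2, add the period and the most recent treatment.
4. Flag findings already present pre-application, and show them with the preceding period's treatment without ruling that treatment out as a cause.

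The cost is SAP wording, one descriptive table, extra columns in Table 14 and Listing 2, and counts that may be small. No new examination is needed.

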9.3.2 Oral Hard Tissue Examination

Where possible, this procedure should be conducted by a single dental examiner or clinically qualified designee for all subjects. Examination of the oral hard tissues (all facial, lingual/palatal, mesial/distal and occlusal surfaces) will only be carried out on a subject's mandibular dentition (as applicable) and will be accomplished by direct/indirect observation, using retraction aids as appropriate. Enamel irregularities, tooth fracture, defective/faulty restorations (all direct & indirect restorations including fixed/removable prostheses), carious lesions, non-carious hard tissue loss (abrasion, attrition, abfraction and erosion), and any other hard tissue irregularity (e.g. hypo/hypermineralisation, decalcification) will be recorded.

Observations will be listed as either absent or present, and conditions noted as present will be described in the CRF. Any abnormality or worsening of a pre-existing condition observed by the clinical examiner or reported by the subject from the OHT examination carried out at Screening, Visit 1, will be recorded as an AE. Findings from the screening examination will be used to determine subject eligibility.

The OHT examination will be performed at the start of Screening, Visit 1, before any adhesive application (if required for mandibular stabilization) and/or commencement of screening BF assessments, and at the end of the last study visit after denture and adhesive removal, and all findings will be recorded in the CRF. The OHT examination should be performed by a suitably qualified dental professional with expertise in prosthodontics. The subject may be asked to perform an oral rinse with water to remove debris from the mouth before or during this examination, at the examiner's discretion.

